### 12. STATISTICAL CONSIDERATIONS

#### 12.1. Study Design

This is a non-randomized, open-label, multicenter, phase II study of palbociclib in combination with tamoxifen in subjects with HR(+)/HER2(-) advanced breast cancer who have not received prior systemic anti-cancer therapies for their advanced/metastatic disease. Palbociclib is taken orally with food at a dose of 125 mg on days 1-21 of each 28-day cycle. Tamoxifen is taken orally at a dose of 20 mg on days 1-28 of the 28-day cycle (i.e., continuously). Treatment will continue until disease progression, unacceptable toxicity, or subject refusal.

It is planned that the data from all centers participating in the trial will be combined, so that an adequate number of subject are available for analysis.

## 12.2. Analysis Datasets

#### **Methods of Statistical Analysis**

The definitions of the study populations are listed below. The appropriate study population for each analysis should be chosen and defined in the protocol.

Population	Definition
Enrolled	This will comprise all subjects who meet the eligibility criteria and are registered onto the study.
Evaluable	This will comprise all subjects who receive at least one cycle of trial drug and either undergo at least one post-baseline assessment or die before any evaluation.
Safety	This will comprise all subjects who received at least a single dose of study drug.

## 12.3. Sample Size

Study endpoint is progression free survival (PFS) as assessed by RECIST v1.1 criteria). Previous studies (31, 32) identified progression free survival with tamoxifen of 13 months in pre-menopausal women and 14.5 months in post-menopausal women in first line treatment for breast cancer. We use a null hypothesis of median PFS 15 months as a conservative choice and the alternative hypothesis of median PFS 25 months (31, 32). Controlling for a probability of one-sided Type I error of 0.05, the proposed sample size will be 48 to achieve an 80% statistical power for detecting this difference, assuming 20% censoring rate due to unevaluable, drop-out, and other lost-to-follow-up. The sample size analysis was conducted using the software PASS 14 (NCSS, Kaysville, Utah, USA.). The test was based on an exponential distribution assumption for single arm studies. The accrual period was assumed to be 24 months and the maximum follow-up 24 months too.

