randomized phase II trial of letrozole with or without palbociclib as first line treatment (PALOMA-1/TRIO-18) was conducted in postmenopausal women with HR+/ human epidermal growth factor receptor 2 negative (HER2-) metastatic breast cancer (12). At the time of the final analysis for progression-free survival (PFS) (median follow-up 29.6 months [95% CI 27.9–36.0] for the palbociclib plus letrozole group and 27.9 months [25.5–31.1] for the letrozole group), 41 PFS events had occurred in the palbociclib plus letrozole group and 59 in the letrozole group. Median PFS was 10·2 months (95% CI 5·7–12·6) for the letrozole group and 20·2 months (13·8–27·5) for the palbociclib plus letrozole group (HR 0·488, 95% CI 0.319–0.748; one-sided p=0.0004). The results of this trial led to FDA approval of palbociclib in combination with letrozole as first line therapy for patients with metastatic breast cancer. The recommended starting dose is 125 mg orally daily for 21 days followed by 7 days off in 28 days cycles in combination with letrozole 2.5 mg orally daily continuously. Most common adverse events from the phase II PALOMA-1 trial were neutropenia (48% grade 3), leukopenia (19% grade 3) and fatigue (36% grade 2) (12). Notably, despite the increased incidence of neutropenia, no neutropenic fever was reported. Dose delay was required in 45 % of patients in the combination arm and dose reduction was required in 40% of patients. Findings from the confirmatory trial PALOMA-2, a randomized phase III trial of palbociclib plus letrozole versus placebo plus letrozole for the first-line treatment of post-manopausal patients with ER+/HER2- advanced breast cancer is expected to be reported later this year. In second line setting, palbociclib plus fulvestrant demonstrated an improvement in PFS compared with placebo plus fulvestrant in the PALOMA-3 phase III trial (13). The median PFS was 9.2 months for the palbociclib-containing regimen and 3.8 months for the fulvestrant plus placebo arm.

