#### 3.1. Inclusion Criteria

Subjects must meet all of the following applicable inclusion criteria to participate in this study:

**3.1.1** Male or female  $\geq$  18 years of age at time of consent.

**NOTE**: Both pre- and post-menopausal women are eligible.

Pre-menopausal status is defined as either:

- -Last menstrual period within the last 12 months
- -In case of therapy-induced amenorrhea, plasma estradiol and /or FSH is in the premenopausal range per local normal range.
- **3.1.2** Locally advanced, locoregionally recurrent, or metastatic disease, not amenable to curative therapy. **NOTE**: Although not required as a protocol procedure, a patient with a new metastatic lesion should be considered for biopsy whenever possible to reassess ER/PR/HER2 status if clinically indicated. If a biopsy is prospectively done as part of standard of care, the study would like to store samples for correlative research.
- **3.1.3** Histologically and/or cytologically confirmed diagnosis of ER positive and/or PR positive (ER >1%, PR >1%), HER2 negative breast cancer.

**NOTE**: Subject has HER2-negative breast cancer (based on most recently analyzed biopsy) is defined as a negative in situ hybridization test or an IHC status of 0, 1+ or 2+. If IHC is 2+, a negative in situ hybridization (e.g. FISH, CISH, SISH, DISH, etc.) test is required by local laboratory testing.

**3.1.4** Metastatic disease evaluable on imaging studies. Subjects may have measurable disease as per RECIST 1.1 or bone-only disease.

**NOTE**: Bone-only subjects are eligible if their disease can be documented/ evaluated by bone scans, CT or MRI. Their disease will be assessed using MDA criteria.

**NOTE**: Previously irradiated lesions are eligible as a target lesion only if there is documented progression of the lesion after irradiation.

**3.1.5** No prior systemic anti-cancer therapy for advanced HR+ disease.

**NOTE**: Subjects receiving adjuvant treatment with aromatase inhibitors at time of recurrence are allowed to participate. There is no AI washout period required.

- **3.1.6** Eastern Cooperative Oncology Group (ECOG) Performance Status 0-2
- **3.1.7** Adequate hepatic function within 14 days prior to registration for protocol therapy defined as meeting **all** of the following criteria:
  - aspartate aminotransferase (AST)  $\leq$  2.5 × ULN or  $\leq$  5 × ULN for subjects with known hepatic metastases and

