# 9.3. Compare differences in response for subjects presenting with de novo metastatic breast cancer to subjects that progressed while on aromatase inhibitors.

There will be two main subject populations in this trial: subjects that present with de novo metastatic disease and subjects that will progress while on adjuvant endocrine therapy with aromatase inhibitors. Looking at differences in response between these 2 groups could provide further information about the mechanism for endocrine resistance.

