## 12.4. Analysis of Primary Objectives/Aims

The primary objective of the Phase II study is to estimate the activity of the combination of palbociclib and tamoxifen in first line therapy for subjects with HR(+)/HER2(-) advanced breast cancer who have not received prior systemic anti-cancer therapies for their advanced/metastatic disease, evaluated by progression-free survival (PFS) using RECIST 1.1 in subjects with HR(+)/HER2(-) advanced breast cancer who have not received prior systemic anti-cancer therapies for their advanced/metastatic disease treated with palbociclib in combination with tamoxifen. Median PFS times will be computed, and PFS rate will be calculated with associated 95% confidence intervals. Kaplan-Meier curves will be plotted. Data will be analyzed using the PROC FREQ and PROC LIFETEST in SAS.

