### 12.6. Analysis of Correlative Endpoints, if funding is secured

- Perform proteomic analysis of plasma exosomes to identify potential mechanisms of primary and secondary resistance to tamoxifen/palbociclib.
- Analyze tumor specimens for protein expression of candidate markers of primary resistance.
- Compare difference in response for subjects presenting with de novo metastatic breast cancer to subjects that progressed while on aromatase inhibitors
- Compare differences in response and toxicity profile in African American and Hispanic subjects to Caucasian subjects
- Compare differences in response and toxicity profile between pre- and post-menopausal women.

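### Does the single 15-month PFS null in section 12.3 need a separate benchmark for patients progressing on adjuvant aromatase inhibitors?

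*Combined protocol and SAP*

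**What the plan says.** Section 12.3 cites first-line tamoxifen results by menopausal status ("Previous studies (31, 32) identified progression free survival with tamoxifen of 13 months in pre-menopausal women and 14.5 months in post-menopausal women") and then states: "We use a null hypothesis of median PFS 15 months as a conservative choice". The alternative is 25 months. With one-sided alpha 0.05, 80% power, a 20% loss allowance, 24 months of accrual and 24 of follow-up, it arrives at 48 patients.

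Section 9.3 describes the case mix differently: "There will be two main subject populations in this trial", namely de novo metastatic patients and "subjects that will progress while on adjuvant endocrine therapy with aromatase inhibitors". Section 3.1.5 admits the second group: "Subjects receiving adjuvant treatment with aromatase inhibitors at time of recurrence are allowed to participate".

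Section 12.4 pools everyone: "Median PFS times will be computed, and PFS rate will be calculated with associated 95% confidence intervals". The only planned contrast of the two groups is in 9.3 and 12.6 ("Compare difference in response for subjects presenting with de novo metastatic breast cancer to subjects that progressed while on aromatase inhibitors"). It concerns response rather than PFS, names no method, and depends on funding. The synopsis says that earlier studies found 15 months with tamoxifen, whereas 12.3 reports 13 and 14.5 and presents 15 as a choice.

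**The concern.** The null is split by one factor (menopausal status), while the protocol says its population is split by another (prior AI exposure). Relapse during adjuvant endocrine therapy suggests endocrine resistance, and section 1.2 makes these patients part of the rationale. The background in section 1.1 shows how far medians can move between settings. Palbociclib plus letrozole gave 20.2 months first line against 10.2 for letrozole alone. In second line, "The median PFS was 9.2 months for the palbociclib-containing regimen and 3.8 months for the fulvestrant plus placebo arm".

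If AI-progressing patients have shorter PFS on any regimen, a pooled median falls as their share grows, even if the planned hazard ratio of 15/25 = 0.60 is achieved in both groups. An active combination could then look no better than 15 months.

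**Working it through.** **1. The plan's own figure.** Inputs are from 12.3; PFS is exponential.

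- Events: (1.645 + 0.842)² / ln(25/15)² = 23.7.
- Probability of an event, with L = ln2/m: P(m) = 1 − (e^(−24L) − e^(−48L))/(24L). P(25) = 0.625, reading the follow-up as 24 months after accrual closes.
- Evaluable: 23.7/0.625 = 37.9, so 38. Enrolled: 38/0.8 = 47.5, so 48. This matches the plan.
- With 48 × 0.8 = 38.4 evaluable, D = 24.0 events and power = Φ(√24.0 × ln(25/15) − 1.645) = 0.804.

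**2. Adding a worse-prognosis group.** Let a share p have combination median m₂ and the rest 25 months. Then D = 38.4[(1−p)P(25) + pP(m₂)], the rate-based median M is the event-weighted mean of 25 and m₂, and power = Φ(√D × ln(M/15) − 1.645).

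Example, p = 0.25 and m₂ = 15: D = 38.4[0.75 × 0.625 + 0.25 × 0.801] = 25.7; M = 22.0; power = Φ(5.07 × 0.383 − 1.645) = 0.62.

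| m₂ (months) | Power, p = 25% | Power, p = 50% |
|---|---|---|
| 25 | 80% | 80% |
| 20.2 | 73% | 65% |
| 15 | 62% | 38% |
| 9.2 | 42% | 7% |

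Simulation agrees closely except in the last row, where it gives 37% and 5%. The documents give neither p nor m₂. The shares and the 15 months are assumptions. The 20.2 is a letrozole result and the 9.2 a second-line fulvestrant result, so neither is a value for this group.

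**3. What the table holds fixed.** The 25 months in 12.3 is a median for the whole trial, but the table pins the remaining patients at exactly 25. By the same formula, at p = 25% power is back to 80% if the others reach 26.8 months (m₂ = 20.2) or 29.7 months (m₂ = 15).

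**4. Direction of error.** Suppose tamoxifen alone gives 15 months in the others and 12 in the AI group. Simulated rejection against 15 (38 patients) is 1.8% at a 25% share and 0.9% at 50%, against about 4% when both groups are at 15. The pooled null does not inflate false positives.

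**5. The alternative.** Use a one-sample log-rank test with nulls of 15 and m₀ and a hazard ratio of 0.60 in both groups. Power is Φ(√D × ln(1/0.6) − 1.645), where D uses medians 25 and m₀/0.6. Results at 25% and 50% shares:

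- m₀ = 5.5: 84% and 87%
- m₀ = 9: 83% and 85%
- m₀ = 12: about 82% in both

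Type I error stays near 5% only if m₀ is right. Simulated with 38 patients, no treatment effect and the others truly at 15:

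| AI null used | True AI median | Type I error, p = 25% | Type I error, p = 50% |
|---|---|---|---|
| 9 | 12 | about 11–12% | about 21% |
| 5.5 | 9 | about 23–24% | about 50% |

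**6. Precision by group.** Half the trial is 24 enrolled and about 24 × 0.8 × 0.625 = 12 events. The 95% interval around a 25-month median is 25 × exp(±1.96/√12) = 14 to 44 months.

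**The case for a change.** The best case for a change is that the protocol itself singles this group out, in the rationale (1.2) and again in 9.3, and then sizes the trial as though the group did not differ. Section 12.3 ties neither 13 nor 14.5 months to a particular reference, arm or agent, so a reader cannot tell whether AI relapses are in those figures. Even the mild case (20.2 months) falls below 80% power. Prior therapy is recorded at screening (7.1.1), so a split would need no new data.

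The documentary part of this stands: the share, the benchmark and the sourcing are not stated, and PFS by group is not planned. The inference that 15 months is the wrong null does not. Section 3.1.5 makes all patients first line for advanced disease, which is the setting 12.3 claims for its figures, and those figures may already come from mixed populations.

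Separate nulls are also no clean repair:

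- They rest on a benchmark the documents do not contain.
- The two groups do not cover eligibility. Relapse after adjuvant therapy has ended is admitted, including after tamoxifen stopped more than 12 months earlier (3.2.5), and such patients would have no null.
- Section 9 describes blood collection, including at progression, in the past tense. Changing the primary null of an open-label trial at that stage would be open to the charge of hindsight.

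**Conclusion.** No change is needed. The sample size is correct on its inputs, and the documents do not show that 15 months is wrong for the enrolled mix or that 80% power is missed. The possible loss runs from nothing (AI group also at 25 months) to severe (9.2 months at a 50% share), and where it falls depends wholly on assumed shares and medians. In every case the error is towards missing an effect. A 15-month null that sits above both cited figures is a fair trade against group-specific nulls, which recover power only by risking a type I error of 11% to 50% in the cases simulated.

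The rest is minor. The synopsis wording about 15 months is a clerical slip that 12.3 resolves. The expected mix and the source arms are missing detail. A Kaplan-Meier summary of PFS by prior-therapy group is something analysts can produce from data already collected. It would be imprecise and would leave the pooled estimate in 12.4, and its conclusion, unchanged. This judgement would shift only if the cited tamoxifen figures were shown to exclude AI relapses and a reliable benchmark for that group were available.

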## 12.4. Analysis of Primary Objectives/Aims

The primary objective of the Phase II study is to estimate the activity of the combination of palbociclib and tamoxifen in first line therapy for subjects with HR(+)/HER2(-) advanced breast cancer who have not received prior systemic anti-cancer therapies for their advanced/metastatic disease, evaluated by progression-free survival (PFS) using RECIST 1.1 in subjects with HR(+)/HER2(-) advanced breast cancer who have not received prior systemic anti-cancer therapies for their advanced/metastatic disease treated with palbociclib in combination with tamoxifen. Median PFS times will be computed, and PFS rate will be calculated with associated 95% confidence intervals. Kaplan-Meier curves will be plotted. Data will be analyzed using the PROC FREQ and PROC LIFETEST in SAS.

### 12.5. Analysis of Secondary Endpoints

Characterize safety and tolerability of palbociclib and tamoxifen in first line therapy for subjects with HR(+)/HER2(-) advanced breast cancer who have not received prior systemic anti-cancer therapies for their advanced/metastatic disease.

 Proportion of subjects with each grade of adverse events as defined by CTCAE v4 will be computed along with 95% confidence intervals, and reported in a tabular and descriptive manner.

Assess response rate based on RECIST 1.1 or MDA Criteria. The response rate (complete or partial response) and 95% confidence interval for the response rate will be computed using PROC FREQ in SAS (Cary, NC).

Evaluate clinical benefit rate RR (complete, partial response, or stable disease) based on RECIST 1.1 or MDA Criteria in subjects with HR(+)/HER2(-) advanced breast cancer who have not received prior systemic anti-cancer therapies for their advanced/metastatic disease treated with palbociclib in combination with tamoxifen.

• Clinical benefit rate (complete, partial response, or stable disease) will be assessed every 8 weeks +/- 1 week while on study treatment using RECIST 1.1 (section 8) or MDA Criteria (for patients with bone only disease). Response will be recorded as disease control rate (DCR), or stable disease plus partial response plus complete response, and reported via waterfall plot. The response rate and 95% confidence interval for the response rate will be computed using PROC FREQ in SAS (Cary, NC).

Measure 2-year overall survival (OS) in subjects with HR(+)/HER2(-) advanced breast cancer who have not received prior systemic anti-cancer therapies for their advanced/metastatic disease treated with palbociclib in combination with tamoxifen.

Median OS times will be computed, and OS rate will be calculated with associated 95% confidence intervals. Kaplan-Meier curves will be plotted. Data will be analyzed using the PROC FREQ and PROC LIFETEST in SAS.

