# STUDY SYNOPSIS

TITLE	A Single Arm Phase II Study of Palbociclib in Combination with Tamoxifen as				
	First Line Therapy for Metastatic Hormone Receptor Positive Breast Cancer: Big Ten Cancer Research Consortium BTCRC-BRE15-016				
PHASE	Phase II				
OBJECTIVES	Primary Objectives:				
OBJECTIVES	To estimate the activity of the combination of palbociclib and tamoxifen in first line therapy for subjects with HR(+)/HER2(-) advanced breast cancer who have not received prior systemic anti-cancer therapies for their advanced/metastatic disease, assessed by progression free survival (PFS)				
	Secondary Objective(s):				
	To evaluate:				
	safety and tolerability				
	
 
response rates (complete or partial response) (RR) based on RECIST 1.1 or MDA Criteria (for patients with bone only disease)
 
				
	• clinical benefit rate (CBR; complete, partial response, or stable disease lasting 24 weeks or longer) based on RECIST 1.1 or MDA Criteria				
	• 2-year overall survival (OS)				
	Correlative Objectives, if funding is secured:				
	Perform proteomic analysis of plasma exosomes to identify potential				
	mechanisms of primary and secondary resistance to tamoxifen/palbociclib.				
	
 
Analyze tumor specimens for protein expression of candidate markers of primary resistance.
 
				
	
 
Compare difference in response for subjects presenting with de novo
 
				
	metastatic breast cancer to subjects that progressed while on aromatase inhibitors				
	Compare differences in response and toxicity profile in African American and Hispanic subjects to Caucasian subjects				
STUDY DESIGN	Single arm phase II study				
TOTAL NUMBER OF SUBJECTS	Up to 48 subjects				
KEY ELIGIBILITY	1. Age ≥ 18 years				
CRITERIA	2. Locally advanced, locoregionally recurrent, or metastatic disease, not amenable to curative therapy				
	3. Histologically and/or cytologically confirmed diagnosis of ER positive and/or PR positive (ER>1%, PR>1%), Her2 negative breast cancer				
	4. No prior systemic anti-cancer therapy for advanced HR+ positive disease				
	5. Eastern Cooperative Oncology Group PS 0-2				
	6. Life expectancy greater than 4 months				
	7. Pre or postmenopausal women are eligible				
	8. Adequate hematologic function, as defined as meeting all three of the following criteria:				
	a. Absolute neutrophil count (ANC) $\geq 1.5 \times 10^9 / L$ , and				
	b. Platelets $\geq 100 \times 10^9 / L$ , and				

	77 111 (771) 00 (17

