# 2.1.2. Secondary Objectives

- Characterize safety and tolerability of palbociclib and tamoxifen in first line therapy for subjects with HR(+)/HER2(-) advanced breast cancer who have not received prior systemic anti-cancer therapies for their advanced/metastatic disease.
- Evaluate response rates (complete or partial response) (RR) per local assessment and RECIST 1.1 or MDA criteria in subjects with HR(+)/HER2(-) advanced breast cancer who have not received prior systemic anti-cancer therapies for their advanced/metastatic disease treated with palbociclib in combination with tamoxifen.
- Evaluate clinical benefit rate RR (complete, partial response, or stable disease, lasting 24 weeks or longer) based on RECIST 1.1 or MDA criteria in subjects with HR(+)/HER2(-) advanced breast cancer who have not received prior systemic anti-cancer therapies for their advanced/metastatic disease treated with palbociclib in combination with tamoxifen.
- Measure overall survival (OS) at 2 years in subjects with HR(+)/HER2(-) advanced breast cancer who have not received prior systemic anti-cancer therapies for their advanced/metastatic disease treated with palbociclib in combination with tamoxifen.

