## 7.3. Every two cycles ( $\pm 7$ days)

- Disease assessment will be performed every 2 cycles starting at cycle 3 (cycle 3, 5, 7, etc.) for the first 19 cycles (18 months):
  - o CT/MRI chest, abdomen, pelvis (±7 days).
  - o Whole body bone scan if positive for mets at screening or if clinically indicated.

- o If bone lesion detected from whole body bone scan, repeat bone scan, bone X-ray, CT, or MRI of the largest skeletal lesion identified.
- o If skin lesion detected by physical exam at screening, skin color photography.
- Subjects will be assessed every 2 cycles starting after cycle 5 (cycle 7, 9, 11, etc.):
  - o Physical exam, weight
  - o Vital signs
  - o ECOG performance status
  - o Blood chemistries (sodium, potassium, serum creatinine calcium, albumin, ALT, AST, bilirubin, alkaline phosphatase)
  - o Platelets, ANC and hemoglobin
  - Pregnancy test for women of childbearing potential (WOCP), if clinically indicated. If the urine test is positive or cannot be confirmed as negative, a serum pregnancy test will be required.
  - o Assess adverse events
  - Concomitant medications
  - o Dispense 2 cycles of Palbociclib
  - o Prescribe Tamoxifen (commercial supply)

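### Section 12.5 drops the 24-week requirement from clinical benefit and analyses a disease control rate that the objectives do not declare

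*Combined protocol and SAP*

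**What the plan says.** The endpoint is declared twice with a duration. The synopsis lists "clinical benefit rate (CBR; complete, partial response, or stable disease lasting 24 weeks or longer" and section 2.1.2 has "Evaluate clinical benefit rate RR (complete, partial response, or stable disease, lasting 24 weeks or longer". The second adds a comma before the duration, so it is unclear whether 24 weeks attaches to stable disease (SD) alone or also to complete and partial response (CR, PR).

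Section 12.5 restates the objective without any duration and then says "Clinical benefit rate (complete, partial response, or stable disease) will be assessed every 8 weeks +/- 1 week while on study treatment". The next sentence fixes what is recorded: "Response will be recorded as disease control rate (DCR), or stable disease plus partial response plus complete response, and reported via waterfall plot". A proportion with a 95% confidence interval from PROC FREQ follows.

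On who is analysed, section 12.2 says "The appropriate study population for each analysis should be chosen and defined in the protocol". Section 12.5 names no population for this endpoint.

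**The concern.** The section that an analyst will program from gives a different endpoint from the one declared. It can be read in two ways, and neither is tied to the objective.

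- **Best response.** Anyone whose best response is SD or better counts. On a common denominator this rate can only equal or exceed the declared CBR, because every subject with declared clinical benefit also has disease control.
- **Per visit.** If the rate is taken at an 8-weekly assessment, the section does not say which one. An early visit gives a rate above the declared CBR, week 24 a rate close to it, and a later visit a lower one.

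Two analysts following 12.5 could report different rates, and neither need match the objective. In a single-arm trial no concurrent control shares the same lenient definition, so the choice moves the reported result directly. The denominator is open as well. The Evaluable set takes subjects who "receive at least one cycle of trial drug and either undergo at least one post-baseline assessment or die before any evaluation", which leaves out living subjects with no post-baseline assessment.

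**Working it through.** **1. Search for a rule that restores the duration.** Section 8.2 (RECIST) and section 8.6 (MDA) define SD with no minimum duration. Section 8.3 defines best overall response. Section 8.4 defines objective response rate and PFS, but not CBR. Disease control rate otherwise appears only in the abbreviation list and is not an objective. No passage in section 8 or 12 brings back the 24 weeks.

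**2. Test case.** Section 7.3 states: "Disease assessment will be performed every 2 cycles starting at cycle 3 (cycle 3, 5, 7, etc". With 28-day cycles, Day 1 of cycles 3, 5 and 7 falls at weeks 8, 16 and 24. Take a subject with SD at week 8, progression at week 16 and no response. The best-response reading of 12.5 counts a success; the synopsis and 2.1.2 count a failure.

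**3. Size.** The plan states no expected CBR, so there is no figure to reproduce for this endpoint. The illustration uses the section 12.3 model: "The test was based on an exponential distribution assumption for single arm studies", with median PFS of 15 months (null) and 25 months (alternative) and 48 subjects. That model was first checked against the plan's sample size:

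- events = (1.645 + 0.842)² / [ln(25/15)]² = 23.7
- event probability under the alternative, with 24 months' accrual and 24 months' further follow-up, = 0.625
- 23.7 / 0.625 = 37.9, and 37.9 / 0.80 = 47.4, rounded up to 48, as stated.

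Progression-free proportion: S(t) = exp(−ln 2 × t / median), with weeks converted to months by 7/30.4375. Week 8 is 1.84 months and week 24 is 5.52 months.

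| Week | Median 15 months | Median 25 months |
|---|---|---|
| 8 | 91.8% (44 of 48) | 95.0% (46 of 48) |
| 16 | 84.4% | 90.3% |
| 24 | 77.5% (37 of 48) | 85.8% (41 of 48) |
| 32 | 71.2% | 81.5% |

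Gap between weeks 8 and 24:

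- median 15: 0.9185 − 0.7749 = 0.1436, × 48 = 6.9 subjects
- median 25: 0.9503 − 0.8581 = 0.0922, × 48 = 4.4 subjects

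For scale, exact (Clopper–Pearson) 95% intervals are 63–88% for 37/48 and 80–98% for 44/48.

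**4. Scan window.** At weeks 23 and 25, S = 78.3% and 76.7% (median 15), or 86.4% and 85.3% (median 25). The ±1-week window moves the rate by less than one point each way, so it matters far less than the missing duration.

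**The case against.** The best defence is that 12.5 abbreviates a definition given consistently in both places that declare the endpoint, so the intended CBR can be recovered. This does not hold: 12.5 renames the quantity and supplies its own formula, which is an instruction and not shorthand.

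Other points have more force.

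- The 8-weekly phrase reads more naturally as an assessment schedule, and 12.5 computes a single rate. Best response is thus the likelier reading. The per-visit reading still has literal support, and the mismatch exists under both.
- The 9 to 14 points are illustrative. They ignore the plan's 20% censoring allowance, treat every progression-free subject as having benefit, and apply a RECIST-based curve to an endpoint that also uses MDA criteria. If 24 weeks binds only SD, early responders count whatever their duration and the gap shrinks by an amount that cannot be computed here.
- Scans are tied to cycle days and cycles can slip. If Cycle 7 Day 1 fell at week 28 (an assumption), the model gives 74.3% and 83.6%, which is 2 to 3 points below week 24. This is why the 24 weeks should be counted from treatment start and not from the cycle number.
- A subject who stops treatment early without progression may have no week-24 scan. Section 7.7 describes follow-up for survival only, although the study calendar marks CT/MRI in long-term follow-up. A counting rule is therefore needed.
- The unnamed analysis set affects other endpoints in section 12 too. That is true, but it does not remove the gap here.

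**Conclusion.** The point holds. Followed as written, section 12.5 yields a disease control rate under the name of clinical benefit, and the 24-week condition in the synopsis and 2.1.2 is lost. Under the best-response reading the error always runs in the favourable direction. Its size is about 9 points (25-month median) to 14 points (15-month median), or 4 to 7 of 48 subjects. This assumes exponential PFS, no dropout, all subjects evaluable, and the duration applied to every response category; it is near the upper end for fully evaluable subjects. The consequence is confined to one descriptive secondary endpoint. It should be fixed before analysis, so that nobody later has to choose between a higher and a lower rate.

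**What to change.** - Put the 24-week requirement back into section 12.5 and use one definition in the synopsis, 2.1.2 and 12.5. State whether it applies to SD only or also to CR and PR.
- Count 24 weeks from treatment start, and say how an assessment within ±1 week of the nominal week-24 scan (Cycle 7 Day 1) is treated.
- Name the section 12.2 population used, and say how its members without a week-24 assessment are counted. Counting them as without clinical benefit is the conservative option.
- Apply the PROC FREQ proportion and 95% interval already planned to this CBR.
- If a disease control rate is wanted, report it separately under its own name. Keep the waterfall plot for individual percentage change in lesion size, since it does not display a rate.

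The cost is wording plus one counting rule. The planned response assessments serve both rates, so no new data are needed. The drawback for the sponsor is that the reported CBR will be equal to or lower than a best-response disease control rate.
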